13.4 Methods of Analysis

13.4.1 Primary Outcome Measure

13.4.1.1 Primary Safety Outcome Measure

The number and proportion (Clopper-Pearson exact 95% CI) of subjects having been exposed to BAX 855 who develop inhibitory antibodies to FVIII (≥ 0.6 BU) will be provided.

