#### 5.8 Statistical Tests

The default significance level is to be 5%; confidence intervals are to be 95% and all tests are to be two-sided, unless otherwise specified in the description of the particular analyses.

P-values obtained from statistical inference tests are to be presented using four decimal places. P-values smaller than 0.0001, are to be presented as "<0.0001" and p-values

larger than 0.9999, but les than 1, are to be presented as ">0.9999". A p-value of exactly 1 is to be presented as "1.0000".

Unless otherwise specified the default summary statistics for quantitative variables are to be as follows:

- The number of subjects in each category (n).
- Mean
- Standard deviation (SD).
- First quartile (Q1).
- Median.
- Third quartile (Q3).
- Inter quartile range (IQR) calculated as Q3 Q1.
- Minimum.
- Maximum.
- The number of subjects (n) with missing or unavailable results for quantitative variables is to be presented as "Not reported" where applicable. A "Not reported" category is only to be presented should there be unavailable results. No distinction based on the reason for unavailable results are to be made in any presentations.

If the original data has N decimal places (as derived from the raw data) (i.e., decimal precision [N]) then the summary statistics are to contain the following decimal places (with a maximum of three decimals, unless data warrants the use of more decimals):

- Minimum and maximum: N.
- Mean, median, Q1, Q3 and IQR: N+1.
- Standard deviation: N+2.

For qualitative variables the number (n) and percentage (%) of subjects in each category are to be the default summary presentation. Unless otherwise specified, percentages are to be calculated relative to the total number of subjects in the relevant analysis set as described in the latest version of the Output Templates. In the event of unavailable assessments a "Not reported" category is to be presented. A "Not reported" category is only to be presented if applicable. The "Not reported" category is to be presented with a percentage so that the sum of the percentages of all categories, including the "Not reported" category, totals 100%. No distinction based on the reason for unavailable results are to be made in any presentations.

All values are to be rounded using the SAS® function ROUND. All computed percentages are to be presented using one decimal place.

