#### 8.3 Inhibitor/Antibody Development

FVIII inhibitory antibody development is considered one of the co-primary objectives of this study. Other antibody results are considered part of the secondary objectives of this study.

Results on inhibitory antibodies to FVIII and binding antibodies to FVIII, PEG-FVIII and PEG (both IgG and IgM) and anti-CHO antibodies are to be obtained from the central laboratory.

A subject is to be considered to have developed inhibitory antibodies to FVIII if the result obtained from the central laboratory are  $\geq 0.6~\mathrm{BU}$ .

For the purpose of analyses, positive is considered to be a worse result than a negative result.

Descriptive statistics and listings on inhibitory antibodies to FVIII and binding antibodies to FVIII, PEG-FVIII and PEG and anti-CHO antibodies are to be presented for the SAS. Summaries are to be presented by age categories.

The proportion of subjects which developed inhibitory antibodies to FVIII at any time during the study is to be reported, together with exact Clopper-Pearson 95% confidence intervals for the proportion. The subset of subjects included in this analysis are:

- Subjects that developed inhibitory antibodies to FVIII at any time during the study; and
- Subjects that did not develop any inhibitory antibodies to FVIII but had 100 or more EDs to BAX 855 across all BAX 855 studies AND had a FVIII inhibitory antibody test result from the central laboratory after the 100th ED.

The SAS® code to be used in the Clopper-Pearson analysis:

```
PROC FREQ DATA = <ds>;
  WEIGHT <count>;
  TABLES <result> / BINOMIAL (EXACT CP) ALPHA = 0.05 CL;
RUN;
QUIT;
```

where <ds> refers to the input dataset, <count> the number of subjects with particular result and <result> to the actual result, i.e., "Yes" or "No".

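### Under PROC FREQ defaults, the code prescribed in SAP 8.3 for the co-primary inhibitor proportion prints the proportion without inhibitors, and the SAP does not say to take the complement

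*SAP*

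**What the plan says.** Inhibitor development is the co-primary safety outcome. Protocol 13.4.1.1 plans to report "The number and proportion (Clopper-Pearson exact 95% CI) of subjects having been exposed to BAX 855 who develop inhibitory antibodies to FVIII", using a threshold of 0.6 BU. SAP 8.3 agrees in its text: "The proportion of subjects which developed inhibitory antibodies to FVIII at any time during the study is to be reported". For the interval, the same sentence of the SAP specifies "together with exact Clopper-Pearson 95% confidence intervals for the proportion". It also defines who enters the denominator: subjects who developed an inhibitor, plus subjects who did not but had at least 100 exposure days and an inhibitor test after the 100th.

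SAP 8.3 then gives the SAS code for this analysis, and presents it as the code to use rather than as an example. Its three working lines are "PROC FREQ DATA = <ds>", "WEIGHT <count>" and "TABLES <result> / BINOMIAL (EXACT CP) ALPHA = 0.05 CL". The placeholders are explained as "<count> the number of subjects with particular result and <result> to the actual result", with Yes and No as the two values.

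The code has no `LEVEL=` on the BINOMIAL request, no `ORDER=` on the PROC statement and no `ZEROS` on the WEIGHT statement. Nothing else in SAP 8.3 names the level to report or says what to present if no subject develops an inhibitor. The section does rank a positive result as worse than a negative one, but that does not select a level for the binomial analysis.

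**The concern.** For a one-way table, PROC FREQ computes the binomial proportion for the first level in its ordering unless told otherwise, and it ignores rows with zero weight unless told to keep them. With values Yes and No, the first level is No. The prescribed code would therefore print an estimate and interval for freedom from inhibitors, while the text beside it asks for inhibitor development. If nobody develops an inhibitor, the Yes level is absent from the table.

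Zero cases is a realistic outcome. The documents give no expected rate, but Protocol 6.5 describes the antibody risk in previously treated patients as low, Protocol 6.4.2 reports no inhibitors in the Phase 1 study, and Protocol 9.2 excludes subjects with a current inhibitor or a relevant earlier one. In that case the upper confidence limit is the informative part of the result.

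No hypothesis test or power calculation is attached to this outcome (Protocol 13.1, SAP 2.3), so the proportion and its interval are the whole result. What is at stake is a table that carries the complement under the label of the inhibitor proportion, or a correction improvised at programming time.

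**Working it through.** The documents state no interval or inhibitor rate for this outcome, so there is no planned figure to reproduce. The check is what the code would print against what the text requires.

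**Inputs.**
- Interval: exact Clopper-Pearson, two-sided 95% (SAP 8.3; SAP 5.8, "The default significance level is to be 5%; confidence intervals are to be 95% and all tests are to be two-sided").
- Denominator for illustration: n = 200, the planned evaluable number, and n = 250, the planned enrolment (SAP 2.3). The actual denominator will depend on the SAP 8.3 subset.
- Number of cases x: not given. Values from 0 to 5 are assumed.
- Level analysed by the code: No, because No sorts before Yes and no level is requested (assumed PROC FREQ default).

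**Formulas.** For x cases in n, the lower limit is the 0.025 quantile of Beta(x, n − x + 1), or 0 if x = 0. The upper limit is the 0.975 quantile of Beta(x + 1, n − x), or 1 if x = n. The required result uses x; the printed result uses n − x in its place.

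**Zero cases in closed form.** With x = 0 the upper limit is 1 − 0.025^(1/n).
- n = 200: 1 − 0.025^(1/200) = 1 − 0.981725 = 0.018275, or 1.83%.
- n = 250: 1 − 0.025^(1/250) = 1 − 0.985353 = 0.014647, or 1.46%.

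**Results.**

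| Cases / n | Required (Yes) | Printed by the code (No) |
|---|---|---|
| 0 / 200 | 0% (0 to 1.83%) | 100% (98.17 to 100%) |
| 1 / 200 | 0.50% (0.01 to 2.75%) | 99.50% (97.25 to 99.99%) |
| 2 / 200 | 1.00% (0.12 to 3.57%) | 99.00% (96.43 to 99.88%) |
| 5 / 200 | 2.50% (0.82 to 5.74%) | 97.50% (94.26 to 99.18%) |
| 0 / 250 | 0% (0 to 1.46%) | 100% (98.54 to 100%) |
| 1 / 250 | 0.40% (0.01 to 2.21%) | 99.60% (97.79 to 99.99%) |

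**Tail check.** At the upper limit for 0/200 the probability of no cases is 0.0250. At the upper limit for 1/200 the probability of at most one case is 0.0250, and at its lower limit the probability of at least one case is 0.0250.

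**Relation between the columns.** Clopper-Pearson limits are symmetric under complement: the required lower limit is one minus the printed upper limit, and the required upper limit is one minus the printed lower limit. For 0/200, 100 − 98.17 = 1.83. For 1/200, 100 − 97.25 = 2.75 and 100 − 99.99 = 0.01. Before rounding, the agreement is to machine precision in every row, including those with zero cases.

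**The case against.** A reader might infer that the code fails to deliver the co-primary safety result, or that the upper limit is lost when there are no cases. The documents do not support either reading. The two columns above are one interval expressed in two ways, and neither is biased or wider than the other. With zero cases the required upper limit is one minus the printed lower limit, so it remains available although the Yes level is not shown.

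The governing text is also clear. Target, threshold, analysis subset, interval method and confidence level are all stated in SAP 8.3 and need no change for this point; the code is a placeholder template meant to implement them.

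A mislabelled table would probably be caught. Protocol 13.4.1.1 requires the number of subjects alongside the proportion, SAP 8.3 requires descriptive statistics and listings of inhibitor results, and Protocol 12.1.1.1 makes every confirmed inhibitor a serious adverse event. A figure near 99.5% would conflict with all of these.

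Finally, the point depends on things the documents do not settle. They do not describe PROC FREQ's defaults. If the result were held as a formatted numeric code with the inhibitor level sorting first, the problem would not arise. The Output Templates, which govern presentation, are not among these documents.

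All of this stands, and it limits the severity. It does not remove the inconsistency: the only coding the SAP gives is Yes or No, the code is prescribed, and nowhere does the SAP tell the programmer to subtract from one. Relying on someone noticing leaves the repair of a co-primary result outside the plan. The nearest zero-event rule in the SAP is also a poor guide. For bleeding models in which every count is zero, SAP 7.1 presents zero without a confidence interval. Carried over to inhibitors, that would discard the informative limit.

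**Conclusion.** The point holds as an inconsistency between prescribed code and stated target. Run as written on Yes/No values under PROC FREQ defaults, the code in SAP 8.3 prints the proportion and exact interval for subjects without inhibitors, and with zero cases it shows no Yes level. The text of the same section and Protocol 13.4.1.1 require the opposite proportion.

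The consequence is a risk of misreporting, not a wrong or missing analysis. The required result follows exactly by subtraction, so no estimate, limit or conclusion changes once the right level is reported. Severity is minor to moderate: the discrepancy would probably be noticed, but it affects a co-primary outcome and the plan gives no instruction for resolving it.

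The conclusion rests on two assumptions: that the software takes the first ordered level and drops zero-weight rows by default, which has not been tested in SAS here, and that the variable is stored with the values the SAP names. The illustrative figures also assume 200 or 250 subjects and 0 to 5 cases.

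**What to change.** In SAP 8.3:

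- change the WEIGHT statement to `WEIGHT <count> / ZEROS;`
- request the event level explicitly: `TABLES <result> / BINOMIAL (EXACT LEVEL='Yes') ALPHA = 0.05;`
- state that the input dataset always holds a Yes row, with count 0 if there are no cases
- state that zero cases is reported as 0% with its exact upper limit (1.83% if the denominator is 200)
- before the table is produced, run the code in SAS 9.4, the version named in SAP 11, on dummy data with 0 and 1 cases, and compare the output with the required column above. If the software does not analyse the empty level, specify that the complement of the No interval is reported.

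The cost is two code options, two sentences and a short test run. The data, design, analysis subset and interval method stay as they are.

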#### 8.4 Vital Signs

Information for Vital Signs is to be obtained from the eCRF (Vital Signs eCRF panels).

The following derivations based on eCRF reported results are to be performed:

• A result is considered to be out of range if the observed result is less than the lower limit of the normal range (indicated as "L") or larger than the upper limit of the normal range (indicated as "H"). The normal ranges to be used are:

Parameter	Age Range (Years)				
r ai ainetei	≥13	≥6 - <13	≥3 - <6	<3	
Respiratory rate (breaths/minute)	12-20	14-22	20-25	20-30	
Pulse rate (beats/minute)	60-90	60-95	65-110	70-110	
Systolic blood pressure (mmHg)	90-120	100-120	95-110	90-105	
Diastolic blood pressure (mmHg)	60-80	60-75	60-75	55-70	
Body temperature	35-37.9	35-37.9	35-37.9	35-37.9	

Parameter	Age Range (Years)			
rarameter	≥13	≥6 - <13	≥3 - <6	<3
(°C)				

Summary statistics on observed and change from baseline results are to be presented for vital signs on the SAS by age groups. All vital signs results are to be listed for the SAS.

#### 8.5 Physical Examination

Information for physical examination is to be obtained from the eCRF (*Physical Examination* eCRF panels).

Physical examination results are to be listed for the SAS. No summaries on physical examination are to be presented.

#### 8.6 Comments

Information for comments is to be obtained from the eCRF (*General Comments* eCRF panel).

Comments are to be listed for the ENR. No summaries on comments are to be presented.

#### 9. EVALUATION OF PATIENT REPORTED OUTCOMES

For all patient reported outcomes baseline are to be defined as:

- The baseline measurement for the particular questionnaire in the parent study (i.e., the first study participated in the BAX 855 program of studies); OR
- For BAX 855 naïve subjects or subjects with no baseline results available in the
  parent study, the first questionnaire results prior to first dose in the current study
  are to be defined as baseline.

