10.3.2 BAX 855 Naïve Subjects

BAX 855 naïve subjects will continue using their FVIII concentrate and treatment regimen until baseline/start of prophylaxis, except for one infusion with BAX 855 for PK determination (for subjects receiving a PK-tailored prophylactic treatment regimen).

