20.2.2.2 PK Assessment

For BAX 855 naïve subjects and transitioning subjects with no prior PK assessment

Blood sampling after infusion of BAX 855 for PK assessments will be performed over a 4-day period for subjects aged ≥ 12 years or a 2.5 day period for subjects aged < 12 years. A minimum wash-out period of 84 to preferably 96 hours prior to the PK infusion is required for subjects transitioning from another BAX 855 study and 72 hours prior to PK infusion for BAX 855 naïve subjects on treatment with any other FVIII concentrate, and the subject must not be actively bleeding.

The following assessments will be performed:

Pre-infusion

- Confirmation of eligibility
- Physical examination, including height (for subjects aged < 18 years at enrollment) and body weight
- Review and discuss subject e-diary, including:
 - Review bleeding episodes and their treatment
 - Adverse events
 - Concomitant medications and non-drug therapies
- Laboratory assessments within 30 minutes of start of infusion:
 - FVIII activity and antigen
 - Immunogenicity tests (BAX855 naïve subjects only)
 - TGA parameters and VWF antigen (optional in subjects aged < 12 years)
- Vital signs (within 15 minutes of start of infusion)

Infusion for PK assessment:

- Infusion of 60 ± 5 IU/kg BAX 855

Post-infusion:

- Laboratory assessments in subjects aged ≥ 12 years:
 - FVIII activity, FVIII antigen and TGA parameters at the following post-infusion time points: 15 min \pm 5 min, 3 h \pm 30 min, 9 h \pm 30 min, 32 h \pm 2 h, 56 h \pm 4 h, and 96 h \pm 4 h
- Laboratory assessments in subjects aged < 12 years:
 - FVIII activity and antigen at the following post-infusion time points: 15 min \pm 5 min, 9 h \pm 30 min, 56 h \pm 4 h
 - Optional TGA parameters at the same timepoints
- Vital signs at 30 min \pm 5 min post-infusion

Other procedures:

- Dispense IP to transitioning subjects:
 - A sufficient quantity of IP will be dispensed to cover the period until the next scheduled visit in 6 ± 1 weeks.

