20.2.2.3 Baseline Visit / Start of Prophylaxis

This visit takes place 6 ± 1 weeks following the PK assessment, or following screening if a PK was already available in case of transitioning subjects. This visit will then coincide with confirmation of eligibility. It is the baseline time point for all subsequent visits.

At least 84 to preferably 96 hours must have elapsed since the previous BAX 855 administration and at least 72 hours since the previous administration of any other FVIII concentrate in case of BAX855 naïve subjects, and the subject must not be actively bleeding.

The following procedures will be performed:

Pre-infusion:

- Confirmation of eligibility for transitioning subjects with previous PK data
- Physical examination, including height (for subjects aged < 18 years at enrollment) and body weight
- Review and discuss subject e-diary, including:
 - Review bleeding episodes and their treatment (not applicable for BAX855 naïve subjects)
 - Adverse events
 - Concomitant medications and non-drug therapies
- Laboratory assessments within 30 minutes of start of infusion:
 - FVIII activity and antigen
 - TGA parameters and VWF antigen (optional in subjects aged <12 years)
 - Immunogenicity tests
 - Hematology, clinical chemistry, and lipid panel
- PROs:
 - Bleed and pain severity using Haemo-SYM (≥ 18 years), HRQoL using SF-36 (≥ 14 years), HRQoL using PedsQL (< 14 years), patient satisfaction with treatment using the Satisfaction Questionnaire (all ages), and Patient Activity Level (all ages)
- Vital signs (within 15 minutes of start of infusion)

Determination of IR:

- Infusion of 60 ± 5 IU/kg BAX 855

Post-infusion:

At 30 ± 15 min post-infusion:

- FVIII activity and antigen
- TGA parameters (optional in subjects aged < 12 years)
- Vital signs

Other procedures:

- Dispense IP:
 - A sufficient quantity of IP will be dispensed to cover the period until the next scheduled visit in 4 ± 1 week.

20.2.2.4 Follow-up Visits: At 4 (\pm 1) Weeks, 8 (\pm 1) Weeks, 18 (\pm 2) Weeks from Baseline Visit

No wash-out period is required for this visit and the patient should not be in a bleeding state.

The visit should be performed immediately prior to the next regular prophylactic infusion in order to determine adequate FVIII trough levels.

The following assessments will be performed:

Pre-infusion:

- Physical examination, including height (for subjects aged < 18 years at enrollment) and body weight
- Review and discuss subject e-diary, including:

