## 4.2 Safety Analysis Set (SAS)

The safety analysis set (SAS) is to comprise all subjects in the ENR with at least one BAX 855 infusion. All safety analyses are to be performed on the SAS.

Information on dosing with BAX 855 is to be obtained from the following eCRF panels:

- Study Infusion eCRF panels.
- *Infusion for Determination of Incremental Recovery* eCRF panels.
- Infusion for PK Assessment eCRF panels.
- *Minor Surgery* eCRF panels.

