## 5.3 Reference Start Date and Study Day

Reference start date is defined as the day of the subject's first BAX 855 infusion in the 261302 protocol (henceforth referred to as the current study) and is to be referred to as Day 1. Subjects that discontinue study participation prior to receiving any BAX 855 dose in the current study will not have a reference start date.

Study Day is to be calculated as described below from the reference start date (first BAX 855 infusion in the current study), and is to be used to show start and stop day of assessments and events.

• If the date of the event is on or after the reference date then:

$$Study Day = (Date of Event - Reference Date) + 1$$

• If the date of the event is prior to the reference date then:

Study Day = (Date of Event - Reference Date)

In the situation where the assessment/event date is partial or missing, study day and corresponding durations are not to be calculated.

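### SAP Section 9's PRO baseline rule has no qualifying scheduled questionnaire for naïve subjects who enter directly on PK-tailored dosing, or for transitioning direct entrants without a parent-study PRO

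*SAP*

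**What the plan says.** SAP Section 9 defines PRO baseline in two steps. The baseline from the first BAX 855 study is used if there is one. For naïve subjects, and for subjects with no parent-study baseline, it is "the first questionnaire results prior to first dose in the current study". Section 9 does not say what counts as a dose.

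Elsewhere the SAP is broad. Section 5.3 states: "Reference start date is defined as the day of the subject's first BAX 855 infusion in the 261302 protocol". Section 4.2 lists the "Infusion for PK Assessment eCRF panels" among the sources of BAX 855 dosing data.

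The Protocol sets the visits. Under 10.3.2, naïve subjects stay on their own FVIII product until prophylaxis starts, "except for one infusion with BAX 855 for PK determination". The PK visit (20.2.2.2) specifies "Infusion of 60 ± 5 IU/kg BAX 855" and lists no PROs. PROs first appear at the Baseline/Start of Prophylaxis visit (20.2.2.3): "This visit takes place 6 ± 1 weeks following the PK assessment, or following screening if a PK was already available in case of transitioning subjects".

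**The concern.** The rule needs a questionnaire completed before a given infusion, while the PK-tailored schedule places the first questionnaire after it. A subject without a baseline has no change score. That subject leaves the change-from-baseline summaries, the improvement counts and the Wilcoxon signed-rank tests for Haemo-SYM, SF-36 and PedsQL (SAP 9.1 to 9.3), although observed scores can still be summarized.

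Assessing PROs over time is a stated secondary objective. The gap is tied to regimen and route of entry, and PRO scores and changes are summarized by regimen. The PK-tailored change summaries would therefore lose direct entrants for a reason built into the schedule. The rule also leaves a programmer to choose between dropping these subjects and keeping them, which a prespecified analysis should settle.

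**Working it through.** The SAP states no figure for this point, so the check sets the baseline rule against the visit schedule (Protocol 20.2 and 20.3).

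| Route of entry | First BAX 855 infusion in this study | First scheduled PRO in this study | Meets SAP Section 9? |
|---|---|---|---|
| Naïve, fixed dose | ED1 | ED1, before the infusion (20.2.1.2) | Yes |
| Transitioning, fixed dose | Screening | Screening, before the infusion (20.2.1.1.1) | Yes, if needed |
| Naïve, directly PK-tailored | PK visit | Baseline/Start of Prophylaxis (20.2.2.3) | No |
| Transitioning, directly PK-tailored | Screening | Baseline/Start of Prophylaxis | No, but the parent-study baseline is used if there is one |

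**Naïve direct entrants.** The screening list (20.2.2.1.2) and the PK visit list contain no PROs, and the table in 20.3.3 has its first PRO mark at the Baseline visit. The interval from first infusion to first PRO is 6 ± 1 weeks:

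- shortest: 5 × 7 = 35 days
- nominal: 6 × 7 = 42 days
- longest: 7 × 7 = 49 days

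SAP 5.3 computes study day as the date difference plus 1, so the first PRO falls on study day 36 to 50 (nominally 43). No scheduled questionnaire precedes Day 1.

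**Transitioning direct entrants.** Section 20.2.2.1.1 schedules an infusion at screening and no PRO there. Study BAX 855 is dispensed and dosing continues until the Baseline visit.

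- PK already available: first PRO 35 to 49 days after screening.
- PK still needed: the PK visit is within 45 days of screening, then 6 ± 1 weeks follow, so the first PRO comes up to 45 + 49 = 94 days after screening.

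The gap matters only for those without a parent-study PRO.

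**Is there a fallback?**

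- SAP 5.5 excludes quality-of-life analyses from the general baseline rule.
- SAP 5.4 allows imputation only for body weight, AE causality and severity, and laboratory limits of quantification.
- SAP 6.7 replaces the first infusion by the first prophylactic infusion for PK-guided subjects, but only when deriving the observation period for efficacy.
- SAP 5.7, which lists departures from the Protocol analysis, is silent on PRO baseline.

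**Switchers.** Subjects may move to PK-tailored dosing at any time (20.2.2.1; note a to 20.3.3). A naïve subject who began on fixed dose already has the pre-infusion ED1 questionnaire, which satisfies Section 9 and remains the baseline after the switch.

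**The case against.** The strongest reply is that the dose meant in Section 9 is the first prophylactic one. The term is undefined there. Protocol 10.5.1 and 10.5.2 place the baseline PRO at the start of prophylaxis, the visit is named accordingly, and SAP 6.7 shows the authors setting the PK infusion aside. This may well be the intent, and it makes the defect one of wording, not of data collection. It does not settle the matter: SAP 6.7 is confined to the observation period, and SAP 5.3 and 4.2 point the other way. Nor would that reading cover transitioning direct entrants, who receive study prophylaxis before their Baseline visit.

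A reader might infer that every PK-tailored subject, or every naïve one, lacks a PRO baseline. The documents do not support that. Naïve subjects who switch from fixed dose keep their ED1 questionnaire, transitioning subjects who started on fixed dose have a pre-infusion screening PRO listed, and subjects with a parent-study baseline use that. Whether any transitioning subject lacks one depends on parent protocols that are not available here.

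It is also fair to say that the reach is limited. PROs are secondary, the tests are within-subject before-and-after comparisons on the full analysis set, and no between-regimen PRO test is planned. That limits the consequence but does not supply a baseline.

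**Conclusion.** The concern holds for subjects who enter directly on the PK-tailored regimen: all naïve direct entrants, and any transitioning direct entrants without a parent-study PRO. For naïve direct entrants the first scheduled questionnaire falls 35 to 49 days after the infusion it should precede. Read literally, the rule removes both groups from the PRO change analyses.

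This rests on reading the dose in Section 9 as SAP 5.3 and 4.2 read BAX 855 dosing, and on no unscheduled questionnaire having been completed earlier. The documents do not give the number of subjects affected, so neither the share lost nor any resulting bias can be stated. Neither co-primary endpoint is involved. The SAP should be changed, because a stated rule conflicts with the visit schedule in a secondary analysis and the repair is small.

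**What to change.** Add to SAP Section 9:

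1. Keep the current rule wherever a questionnaire satisfies it: the parent-study baseline, or a questionnaire before the first dose in this study. This includes fixed-dose subjects who later switch to PK-tailored dosing.
2. Where none exists because the subject entered directly on the PK-tailored regimen, use the pre-infusion questionnaire at the Baseline/Start of Prophylaxis visit. This agrees with Protocol 10.5.1 and extends the SAP 6.7 convention.
3. Flag subjects under item 2 as having BAX 855 exposure before baseline, and report how many there are.

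Baseline should not be redefined for everyone as the last questionnaire before the assigned regimen. That would replace a switcher's valid pre-exposure ED1 score with one taken after BAX 855 prophylaxis.

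The cost is a few lines of text and one flag variable, with no new data. The small downside is that baseline for these subjects follows the PK infusion or, for transitioning subjects, earlier prophylaxis, so their change scores do not start from an unexposed state.
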